## 7.2. Definition of Serious Adverse Device Event (SADE)

The SADE is the adverse device effect that has resulted in any of the consequences characteristic of a serious adverse event (SAE).

The FDA definition of a SAE will be used in this study: An AE or suspected adverse reaction is considered "serious" if, in the view of the investigator, it results in any of the following outcomes:

- Death
- A life-threatening adverse event
- Inpatient hospitalization or prolongation of existing hospitalization
- A persistent or significant incapacity or substantial disruption of the ability to conduct normal life functions or,
- A congenital anomaly/birth defect.

Important medical events that may not result in death, be life-threatening, or require hospitalization may be considered serious when, based upon appropriate medical judgment, they may jeopardize the participant and may require medical or surgical intervention to prevent one of the outcomes listed in this definition. All SADEs will be reported to the reviewing IRB as necessary according to their rules.

# 7.3. Definition of Unanticipated Adverse Device Effect (UADE)

Any serious adverse effect on health or safety or any life-threatening problem or death caused by, or associated with, a device, if that effect, problem, or death was not previously identified in nature, severity, or degree of incidence in the investigational plan or application (including a supplementary plan or application), or any other unanticipated serious problem associated with a device that relates to the rights, safety, or welfare of subjects.

# 7.4. Severity of ADE

- Grade 1: Mild; asymptomatic or mild symptoms; clinical or diagnostic observation only; intervention not indicated.
- Grade 2: Moderate; minimal, local or noninvasive intervention indicated; limited ageappropriate instrumental activities of daily living.
- **Grade 3:** Severe or medically significant but not immediately life-threatening; hospitalization or prolongation of hospitalization indicated; disabling; limiting activities of daily living involving self-care.

Medline Industries, LP

An evaluation of the skin protection characteristics of two commercially available skin barrier protectants MED-2022-DIV71-003

08-AUG-2022

Version 2.0 CONFIDENTIAL Page 20 of 28

- Grade 4: Life threatening consequences; urgent intervention indicated.
- **Grade 5:** Death related to ADE.

#### 7.5. Relatedness of ADE and SADE

- Unrelated: This category applies to those ADEs, which after careful consideration, are clearly and incontrovertibly due to extraneous causes (disease, environment, etc.)
- Possible: This category applies to those ADEs for which, after careful medical consideration
  at the time they are evaluated, a connection with the Investigational Product administration
  appears unlikely but cannot be ruled out with certainty.
- Probable: This category applies to those ADEs, which after careful medical consideration at
  the time they are evaluated, are felt with a high degree of certainty to be related to the
  Investigational Product.
- **Definite:** This category applies to those ADEs, which after careful consideration, are clearly and incontrovertibly due to the Investigational Product.

## 7.6. Expectedness

The PI will be responsible for determining whether an ADE or SADE is expected or unexpected. An ADE will be considered unexpected if the nature, severity, or frequency of the event is not consistent with the risk information previously described for the study intervention.

# 7.7. ADE Reporting

The ADEs will be recorded on the ADE form (provided by Medline) by the study personnel and reviewed by the PI. Changes in the severity of an ADE will be documented to allow an assessment of the duration of the event at each level of severity. Changes in severity will necessitate a new CRF to document the new level of severity. ADEs characterized as intermittent require documentation of onset and duration of each episode.

Non-serious ADEs are to be reported to the IRB per IRB reporting requirements.

## 7.8. Serious Adverse Event Reporting or SADE and UADE Reporting

The SADEs and UADEs will be recorded on the SADE form (provided by Medline) by the study personnel and reviewed by the PI. The study personnel or the PI shall submit the completed SADE form to Medline as soon as possible, but in no event later than 48 hours after the PI first learns of the effect. The study personnel or the PI will be responsible for reporting the event to the IRB per the IRB's reporting requirements, and to the FDA if applicable. Thereafter, the study personnel or the PI shall submit additional reports concerning the effect as the FDA requests.

The PI shall complete an SADE Form and submit the form to the IRB as soon as possible, but in no event later than 48 hours after the PI first learns of the event. The PI will be responsible for reporting the event to the IRB per the IRB's reporting requirements, and the FDA if applicable. Thereafter, the PI shall submit any additional reports concerning the event as the FDA requests.

Medline Industries, LP

An evaluation of the skin protection characteristics of two commercially available skin barrier protectants MED-2022-DIV71-003

08-AUG-2022

Version 2.0 CONFIDENTIAL Page 21 of 28

The PI shall complete a SADE Form no later than 48 hours after first learning about the effect. The PI shall report the SADE to the reviewing IRB, if applicable, according to their reporting requirements. The PI, who is responsible for conducting an evaluation of the SADE, shall report the results of such evaluation to the FDA and to all reviewing IRBs if applicable within 10 working days. Thereafter, the PI shall submit such additional reports concerning the effect as FDA requests.

For questions regarding this process or the event, you may contact your Medline Clinical Designee:

Name: [name], MSN, MPH, Clinical Affairs Director

[contact]

E-mail: [contact]

#### 8. STATISTICAL CONSIDERATIONS

#### 8.1. Sample Size Determination

A sample size of 42 was elected for a superiority margin of at least 15 arbitrary capacitance units  $(A.C.U)^{10}$  as measured by the Corneometer® with an estimated mean of pair differences of 17.5 and the standard deviation of 5.05, given the 80% power at Bonferonni adjusted significance level of  $\alpha = .0125$ . Internal evaluation SBP data was used as a starting point, and PASS- Paired T-Tests for Superiority by a Margin procedure was utilized for the sample size estimation (PASS 2021 Power Analysis and Sample Size Software (2021). NCSS, LLC. Kaysville, Utah, USA, ncss.com/software/pass).

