### 8.8. Statistical Analysis

Statistical analyses will be conducted in SAS® software, Version 9.4 or higher of the SAS System for Windows (Copyright © 2013 SAS Institute Inc.) or other appropriate statistical software. P < .05 will be considered statistically significant.

All continuous variables will be summarized for the full sample and by SBP group using the following descriptive statistics: (non-missing sample size), mean, standard deviation, median, maximum and minimum. The frequency and percentages (based on the non-missing sample size)

Medline Industries, LP
An evaluation of the skin protection characteristics of two commercially available skin barrier protectants
MED-2022-DIV71-003
08-AUG-2022

Version 2.0 CONFIDENTIAL Page 23 of 28

of observed levels will be reported for all categorical measures. 95% confidence intervals will be calculated for all means.

Spearman correlation analysis will be used to examine possible associations between the key variables of Marathon® or Cavilon™ use and the Corneometer® measurements at various timepoints with covariates of age, sex, and dominant arm. Additional t-tests or non-parametric tests will be employed to further examine any significant associations found in the correlational analyses between key and covariate measures.

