# **Analysis of Primary Endpoints**

# 8.8.1. Primary Endpoints

Degradation of the SBP over seven days as measured by the Corneometer®.

The breakdown of the SBPs on the volar forearm test areas will reflect the duration of wear of the SBPs. Independent sample t-tests or non-parametric equivalent tests will be used to compare mean Marathon® and Cavilon™ Corneometer® values at baseline (Visit 1), Visit 2, Visit 3, Visit 4, Visit 5, and the final Visit 6 for untreated control area and volar forearm test area measurements. Paired-sample t-tests will be used to compare any two data points for a given SBP and location.

The breakdown of the SBP on the inner elbow test area, relative to the corresponding volar forearm test area, will reflect the durability of the products. Derived variables will be created to calculate the difference between the volar forearm test area measurement and the inner elbow test area measurement at baseline (Visit 1), Visit 2, Visit 3, Visit 4, Visit 5, and the final Visit 6. Independent sample t-tests or non-parametric equivalent tests will be used to compare mean Marathon® and Cavilon™ Corneometer® difference values at baseline (Visit 1), Visit 2, Visit 3 and the final Visit 6 on Day 8. Paired-sample t-tests will be used to compare any two data difference points for a given SBP.

Both degradation and durability endpoints will be graphed across time by SBP with and without 95% confidence intervals of the mean.

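### The sample size is for a paired test of superiority by 15 A.C.U. at alpha .0125, but the products are compared by independent-sample tests with no margin at P < .05, so the stated power and level belong to no planned test

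*Combined protocol and SAP*

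**What the plan says.** Section 8.1 sets the sample size: "A sample size of 42 was elected for a superiority margin of at least 15 arbitrary capacitance units", "with an estimated mean of pair differences of 17.5 and the standard deviation of 5.05", "given the 80% power at Bonferonni adjusted significance level of" .0125. It names the software procedure: "Paired T-Tests for Superiority by a Margin procedure was utilized for the sample size estimation". It does not say whether .0125 is one- or two-sided, which product is expected to be superior, which site and visit the 17.5 and 5.05 describe, or which four tests the Bonferroni divisor counts. It also does not define the pair. Marathon against Cavilon in the same person is the natural reading, because section 6.2.2 puts one product on each arm.

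Section 8.8 gives one significance level: "P < .05 will be considered statistically significant". The .0125 does not reappear.

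Section 8.8.1 gives the product comparison: "Independent sample t-tests or non-parametric equivalent tests will be used to compare mean" Corneometer values. It covers six visits on the forearm test area, six on the untreated control area, and four for the forearm-minus-elbow difference (Visits 1, 2, 3 and 6). No margin is mentioned. Paired tests do appear, but only within a product: "Paired-sample t-tests will be used to compare any two data points for a given SBP and location" and, for durability, "Paired-sample t-tests will be used to compare any two data difference points for a given SBP".

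The primary objective (synopsis and section 3) is to evaluate and compare the products. It states no margin.

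**The concern.** Four elements define the test that was sized: pairing, a 15-unit margin, a level of .0125 and a family of four. None of them is carried into the analysis of the primary endpoint. The sized test and the written test answer different questions. One asks whether the products differ by more than 15 A.C.U.; the other asks whether they differ at all.

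A report could then cite 80% power for superiority by 15 units beside a significant P value that says nothing about 15 units. A reader also could not tell which of the sixteen listed between-product comparisons were meant to be held to .0125. If these choices were settled after the data were seen, they would be open to the charge of being data-driven.

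**Working it through.** **Inputs.** From 8.1: n = 42, margin 15, mean pair difference 17.5, SD 5.05 (read as the SD of the pair differences), alpha .0125. From 8.8: level .05. From 8.8.1: independent-sample test, no margin. Assumed: the pair is product against product, and the between-arm correlation ρ, which the documents do not give, runs from 0 to .8.

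**1. Reproducing 42.** Paired non-central t with effect 17.5 − 15 = 2.5.

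- SE = 5.05/√42 = 0.779; non-centrality = 2.5/0.779 = 3.21; df = 41.
- One-sided .0125: power 79.6% at n = 41 and **80.7% at n = 42**. So 42 is the smallest sample that reaches 80%.
- Two-sided .0125: power 72.2% at n = 42, 79.3% at 48 and 80.4% at 49.

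The arithmetic of 8.1 is sound for a one-sided test.

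**2. Observed difference the sized test needs.** 15 + t(.9875, 41) × SE = 15 + 2.327 × 0.779 = **16.8 A.C.U.** If .0125 is two-sided: 15 + 2.613 × 0.779 = 17.0.

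**3. Observed difference the written test needs.** The SD within an arm is SD_diff/√(2(1 − ρ)). The threshold is t(.975, 82) × arm SD × √(2/42), with t = 1.989. At ρ = .5 the arm SD is 5.05, so the threshold is 1.989 × 5.05 × 0.218 = 2.19.

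| ρ | SD_diff 5.05: threshold | P < .05 at true difference 5 | SD_diff 10.1: threshold | P < .05 at true difference 5 |
|---|---|---|---|---|
| 0 | 1.55 | >99.9% | 3.10 | 88.7% |
| .3 | 1.85 | >99.9% | 3.71 | 79.5% |
| .5 | 2.19 | >99.9% | 4.38 | 65.7% |
| .7 | 2.83 | 99.6% | 5.66 | 35.1% |
| .8 | 3.47 | 96.5% | 6.93 | 13.2% |

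The probabilities are simulated. At SD 5.05 the threshold is 1.55/15 = 10% to 3.47/15 = 23% of the margin. At twice the SD (10.1) the sized test needs 18.6, so the gap remains.

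**4. Is power lost?** No. At a true difference of 17.5 the written test has more than 99.9% power at every ρ in the table and at both SDs. Ignoring positive pairing makes it conservative: its real error at nominal .05 is 4.9% (ρ = 0), 2.0% (.3) and 0.6% (.5).

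**5. Which tests does .0125 cover?** .05/4 = .0125 implies four tests, and 8.8.1 lists 6 + 6 + 4 = 16. The four durability time points could be the divisor, but no text says so. One of them is the baseline, taken before application (section 6.2.3). They also omit Visit 4, the 72-hour reading under the schedule in 6.3.1, although Note 2 of section 4.1 treats the first 72 hours as the more important window. With paired tests at two-sided .0125 and between-test correlation 0 to .9, family-wise error is 5.0% to 2.7% for four tests. For eight (forearm Visits 2 to 6, durability Visits 2, 3 and 6) it is 9.6% to 3.6%.

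**The case against.** The strongest objection is that nothing goes badly wrong. Power at 17.5 is near certain, and the independent-sample test is conservative. With ρ = .5, even eight written tests at .05 have family-wise error of only about 2% to 5%. The study is post-market, no success rule is stated, and 8.8 asks for confidence intervals for all means, so the sizes of effects will be visible. All of this is true. It shows that the problem is not power or, at moderate correlation, inflated error. It does not supply the missing margin, and the intervals in 8.8 are for means by product, not for the paired difference.

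Second, 8.1 never defines the pair. If it meant a difference within one product, the test type would match the paired tests in 8.8.1. But those tests have no margin and no .0125 either, and the product comparison would then have no sample-size basis at all. The mismatch survives both readings.

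Third, .0125 and .05 could be reconciled if Bonferroni-adjusted P values were judged against .05. Section 8.8 mentions no adjustment, and the family of four would still be unnamed.

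Fourth, superiority by a margin is directional and 42 matches the one-sided calculation exactly, so one-sided is very likely what was meant. That is fair. The two-sided figures matter only if the sponsor says otherwise.

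Fifth, the thresholds depend on stopping ρ at .8. At ρ = .9 and SD 5.05 the written threshold is 4.9 A.C.U., and a true difference of 5 is significant with about 55% probability. The 96% is thus not a general lower bound. A threshold of 4.9 is still far below 16.8.

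**Conclusion.** The concern holds, and the plan must be corrected before data are seen. The sample size is correctly computed for a test that the analysis section does not contain. Neither the 80% power nor the .0125 level can be attached to any planned result, and a P < .05 under 8.8.1 does not show superiority by 15 A.C.U. With the 8.1 SD, the observed difference needed is 16.8 for the sized test against 1.6 to 3.5 for the written one.

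These figures assume that the pair is product against product, that 5.05 is the SD of those differences at the tested site and visit, that .0125 is one-sided, and that ρ lies between 0 and .8. Doubling the SD or raising ρ to .9 narrows the gap but does not close it. The study is not shown to be underpowered.

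**What to change.** Amend 8.1, 8.8 and 8.8.1 together:

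1. Make the between-product test in 8.8.1 paired within participant, with the signed-rank test as its non-parametric form.
2. Name at most four primary site-and-visit comparisons governed by .0125, chosen with regard to the first 72 hours. One example is forearm and durability at Visits 4 and 6. Visit 4 would then have to be added to the durability tests; 8.8.1 already derives that difference.
3. State the sidedness, the product direction, and the site and visit that 17.5 and 5.05 describe.
4. Label every other test descriptive.

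Then choose one of two routes:

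- **(a) Keep the margin.** Test H0: mean difference ≤ 15 A.C.U. on the forearm comparisons, once 8.1 confirms that its inputs describe them. Put a margin on the forearm-elbow difference only if 8.1 gives that difference its own mean, SD and power; otherwise test it against zero at .0125. The inputs matter: at n = 42, one-sided .0125 and SD 5.05, an assumed mean of 16 gives 15.9% power.
- **(b) Drop the margin.** Test all named comparisons against zero at two-sided .0125, restate 8.1 for that test, and claim no superiority by 15 units. With 42 participants, 80% power is reached at about 2.7 A.C.U. for SD 5.05, or 3.8 for an illustrative SD of 5.05 × √2 = 7.14.

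The cost is wording. All visits are already scheduled, and no participants are added under (b), or under (a) if .0125 is one-sided. If the margin is kept and .0125 is two-sided, either 49 participants are needed or 8.1 must state about 72% power. The price is a stricter success rule, fewer tests that can be called significant, and possibly a lower stated power for durability.

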#### 8.2. Randomization

This is a single-blind study, with participants blinded to the SBPs that are applied to them. Due to the primary focus on durability of the SBPs, randomization will target dominant versus non-dominant arms, not left versus right. Participants will be randomized to either Marathon® or CavilonTM, and this SBP will be applied to their dominant arm, as defined by the participant. This ensures an equal probability of Marathon® and CavilonTM on both dominant and non-dominant arms. If a participant has incomplete data, the participant will be replaced such that the randomization sequence of the replaced participant will be assigned to the new participant.

### 8.3. Populations for Analyses

The analyses will be performed on the intent to treat (ITT) population which consists of all participants who have complete data for all time points and have completed the survey for the secondary endpoint.

No per protocol, safety, or other analyses groups are planned.

Medline Industries, LP
An evaluation of the skin protection characteristics of two commercially available skin barrier protectants
MED-2022-DIV71-003
08-AUG-2022

Version 2.0 CONFIDENTIAL Page 22 of 28

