#### Note:

- 1. Skin treated with the SBPs will typically have lower measurements than untreated skin. As the SBP breaks down, the corresponding measurements are expected to rise.
- 2. Each participant will commence the study on Monday or Tuesday, which will permit daily readings for the first 72 hours, which is the more important window to evaluate SBP wear time. There will be a two-day break over the weekend, after which study personnel will take Corneometer® measurements either on Monday, or Monday and Tuesday, depending on the participant's start date.

Version 2.0 CONFIDENTIAL Page 14 of 28

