### 5.3. Strategies for Recruitment and Retention

Participants will be recruited from an internal database of Medline employees who have previously participated in studies conducted by Medline, and/or have agreed to be contacted for future studies, as well as via advertisement(s). Potential participants will be screened and enrolled until a total of 42 participants with complete data are obtained.

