### 5.4 Early Withdrawal and Replacement

Participants will be discontinued or withdrawn from study participation at any time if either the participants or the study personnel feel that it is not in the participants' best interest to continue participation.

Participation in the study may end at several critical points:

Medline Industries, LP
An evaluation of the skin protection characteristics of two commercially available skin barrier protectants
MED-2022-DIV71-003
08-AUG-2022

Version 2.0 CONFIDENTIAL Page 15 of 28

- Participant withdraws from the study for any reason.
- Participant is not compliant with study procedures.
- Participant presents with adverse event(s) such that in the opinion of the PI it is in the best interest of the participant to discontinue study participation.
- Protocol violation requiring discontinuation of use of the study product(s).

Based on the above reasons, if any participant withdraws from the study or is dismissed, another participant will be recruited such that the total number of participants who complete the study will be 42. If a participant is being replaced, the randomization sequence associated with the replaced participant will be used for the new participant.

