# 6.3.1 Corneometer® Measurements

The participants will return for daily visits except the weekend. For Visits 2 through 4, participants will be instructed to come to the study room within a  $24 \pm 4$  hours window from the previous day's visit.

During Visit 2 through Visit 5, the average of five Corneometer® measurements of skin capacitance and the standard deviation of the measurements will be taken for each of the untreated control areas and test areas on each volar forearm and inner elbow of the participants. The average of the Corneometer® measurements and the standard deviation of the measurements will be recorded in the CRF.

Note: During the period from Visits 1 through 6, participants will be allowed to bathe their arms using a standardized soap provided by the study personnel and will be asked to minimize scrubbing or any other abrasion of the treated skin. In addition, participants will be instructed not to engage in activities, for eg, sports (eg, tennis) or holding a baby that may cause significant abrasion on one arm and not the other.

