### 8.7. Handling of Missing Values

All missing data will be quantified in the final report and possible biases for any missing data will be reported.

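### The only analysis set is called ITT but admits only participants with complete data and a completed survey, so the primary result is a completers analysis

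*Combined protocol and SAP*

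**What the plan says.** Section 8.3 defines one population, names it intent to treat, and says that it "consists of all participants who have complete data for all time points and have completed the survey for the secondary endpoint". It then states that no per-protocol, safety or other group is planned.

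Recruitment follows the same rule. Section 5.3: "Potential participants will be screened and enrolled until a total of 42 participants with complete data are obtained". Section 5.4: "if any participant withdraws from the study or is dismissed, another participant will be recruited", and the newcomer takes over the replaced person's randomization sequence. Section 8.2 applies this to incomplete data as well.

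On missing values, Section 8.7 says only: "All missing data will be quantified in the final report and possible biases for any missing data will be reported". Section 8.4 requires decisions on each protocol deviation before analysis starts, but defines no set.

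The between-product tests in Section 8.8.1 are made separately at each time point. For control and forearm areas they compare "values at baseline (Visit 1), Visit 2, Visit 3, Visit 4, Visit 5, and the final Visit 6". For durability (forearm minus inner elbow) the between-product test lists baseline and Visits 2, 3 and 6 only. Section 4.1, Note 2, says that the Monday or Tuesday start allows "daily readings for the first 72 hours, which is the more important window to evaluate SBP wear time". Surveys are given at Visits 1, 3 and 6 (Section 6.5).

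**The concern.** Complete data and a completed survey are both known only after randomization. A set defined by them is a completers set, and a reader of the report would wrongly take an ITT result to cover everyone randomized.

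Three things are at stake. First, the label misdescribes the evidence. Second, if leaving the study is related to the difference between the two products within a person, completers are a selected group, and no planned analysis would show it. Third, usable readings are set aside although visit-by-visit tests do not need complete profiles, and these include readings from the window that the protocol ranks highest. The survey condition also ties an instrument-based primary endpoint to a questionnaire that it does not use.

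**Working it through.** **The plan's own number.** Inputs from Section 8.1: margin 15, mean paired difference 17.5, SD 5.05, power 80%, alpha 0.0125, paired t-test for superiority by a margin. The effect above the margin is 17.5 - 15 = 2.5. With the noncentral t distribution and one-sided alpha 0.0125, n = 42 with power 0.807, so the figure reproduces. (Sidedness is not stated; two-sided would need 49.) Since enrollment continues until 42 are complete, the analyzed number equals the planned number.

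**Which visits make up the 72-hour window.** Section 6.3.1: "For Visits 2 through 4, participants will be instructed to come to the study room" within 24 ± 4 hours of the previous day's visit. Visit 4 is thus nominally at 3 x 24 = 72 hours, and Visits 5 and 6 lie beyond it.

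**Readings per participant in the between-product comparisons of Section 8.8.1.**

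- Control and forearm areas: 4 areas x 6 time points = 24 averages.
- Inner elbows: 2 areas x 4 time points = 8 averages.
- Total: 32.
- Only Visit 6 missed: 4 x 5 + 2 x 3 = 26 available.
- Only Visit 5 missed: 4 x 5 + 2 x 4 = 28 available.

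The durability test needs forearm and elbow on both arms at 4 time points, 2 x 2 x 4 = 16 averages. A participant who misses only Visit 5 has all 16. Under Section 8.3 all of these readings are excluded.

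**Share of participants affected.** The documents give no dropout rate, so p, the probability of missing each of Visits 2 to 6, is an assumption. Excluded: 1 - (1-p)^5. Excluded although Visits 2 to 4 are complete: (1-p)^3 x (1 - (1-p)^2). Expected enrollment for 42 completers: 42/(1-p)^5.

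| p | Excluded | Excluded with Visits 2-4 complete | Share of exclusions | Expected enrollment |
|---|---|---|---|---|
| 1% | 4.9% | 1.9% | 39% | 44.2 |
| 2% | 9.6% | 3.7% | 39% | 46.5 |
| 5% | 22.6% | 8.4% | 37% | 54.3 |

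The figures are the same whether visits are missed independently or p is the chance of leaving for good at each visit.

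**What the recovered readings would add at Visit 4.** With independent misses, 42/(1-p)^4 = 43.7, 45.5 or 51.6 participants have a Visit 4 reading. The standard error relative to 42 is (1-p)^2, so it is about 2%, 4% or 10% smaller. With permanent exits the number is 42/(1-p)^2 = 42.9, 43.7 or 46.5 and the gain is about 1%, 2% or 5%. Either way this is precision beyond the plan, not a shortfall made good.

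**Whether another section restores the excluded readings.** Section 8.7 promises counts and a discussion of bias, which is disclosure. Section 8.4 concerns deviations. Neither brings a partial profile into an analysis.

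**The case against.** Much of the case for leaving the plan alone is correct.

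- A reader might infer that the trial loses power. It does not: replacement delivers the 42 complete participants that Section 8.1 calls for.
- A reader might infer that exclusions unbalance the products. They do not: each exclusion removes one arm on each product.
- A reader might infer that the product comparison is biased. The documents do not support that. Bias needs exit to be related to the within-person difference, and they give neither a dropout rate nor any indication of such a link. A shift in Corneometer units could be calculated only by inventing a gap between completers and others.
- A reader might infer that the definition hides device events. Section 8 plans no event analysis for anyone, so that gap does not come from Section 8.3. Events are still recorded, reviewed and reported under Sections 7.7, 7.8 and 9.1.2.
- Not every excluded reading is sound. Section 5.4 also removes participants for non-compliance and for protocol violations.
- Surveys fall on measurement visits, so loss through a missed survey alone is probably uncommon. Section 8.3 also speaks of one survey where three are given, so its reach is an inference.
- Section 8.7 can be read as covering participants outside the analysis set, so it does not contradict Section 8.3.

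What remains is the wrong label, a completeness rule that the tests do not need, an unnecessary survey condition, and no planned analysis of anyone but completers.

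**Conclusion.** The point holds as a defect of definition. As written, the primary result is a completers analysis and should not be reported as ITT. That conclusion rests on the text alone and needs no assumption.

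The effect on the product comparison is unknown in size and direction and may be zero. Exclusions of 4.9% to 22.6% are illustrations over an assumed 1% to 5% miss rate per visit; if everyone attends every visit and completes the surveys, nobody is excluded on these grounds and only the label is wrong. The Visit 5 example takes Section 8.8.1's durability list (baseline, Visits 2, 3 and 6) at face value. The example of a missed survey rests on the natural reading of Section 8.3.

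The change is worth making before analysis because it is cheap and lets the report show whether completers differ from the rest. It is not needed to rescue the planned sample size.

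**What to change.** 1. Rename the Section 8.3 set completers and keep it as a sensitivity analysis.
2. Define the primary set as all randomized participants with a product applied and at least one follow-up reading at Visit 2 or later, including those later replaced and regardless of survey status. A looser rule of any post-application reading would admit people with only the Visit 1 reading, taken shortly after application, and so no degradation data.
3. Compare the products within participant, using all readings available at each visit. A likelihood-based repeated-measures model is one option, with its missing-at-random assumption stated. Account for arm dominance: a replacement reuses the replaced person's sequence, so analyzing both counts that sequence twice.
4. State before analysis, under Section 8.4, how readings affected by non-compliance or a protocol violation are handled.
5. Apply the survey condition to the survey analysis only, and say which of the three surveys it means.
6. List replaced participants with reasons, and device events for everyone treated.

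Cost: revised text and slightly more analysis work, with no extra visits. Replacement can continue. N will vary slightly by visit, and allocation of products to dominant and non-dominant arms may be slightly unequal. Exits that depend on unobserved readings are still not corrected.
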